# Compression bandage selection procedure

The choice to apply 'full compression' versus 'reduced compression' will be dictated by the aetiology of the ulcer, wound assessment etc as per standard care. However, one leg will be bandaged in 'paste' compression and one leg in 'dry' compression, through a process of randomisation, using pre-prepared sealed envelopes.

The two types of compression bandages that will be used in this study are 'standard care' and are:

# a) Paste bandages:

 $S_3F$  – full compression (F): AndoFlex TLC Calamine (Milliken, USA) - a two-layer compression bandage. The first layer is a soft foam layer impregnated with Calamine. The second layer is a cohesive short-stretch bandage.  $S_3R$  – reduced compression (R): AndoFlex TLC Lite Zinc (Milliken, USA), a two-layer

compression bandage. The first layer is a soft foam layer impregnated with Zinc. The second layer is a cohesive short-stretch bandage.

# b) Dry bandages:

**S1F**– full compression: UrgoK2 (URGO, France) - a two-layer compression bandage. The first layer is a short stretch bandage that provides 80% of the compression and a second layer, a long stretch bandage.

**S1R** - Reduced compression (R): UrgoK2 Lite (URGO, France) - a two-layer compression bandage. The first layer is a short stretch bandage that provides 80% of the compression and a second layer, a long stretch bandage.

 $S_2F$  – full compression: Coban2 (3M, USA) - a two-layer compression bandage. The first layer is a foam bandage, and the second layer is a cohesive short-stretch bandage.

**S2R** – Reduced compression (R): Coban2 Lite (3M, USA), a two-layer compression bandage. The first layer is a foam bandage, and the second layer is a cohesive short-stretch bandage.

# Timeline

Each patient participant will be consented at time of recruitment. A patient information sheet will be offered. Each leg will be randomised to either  $S_1F/S_1R$ ,  $S_2F/S_2R$  or  $S_3F/S_3R$ . The Research Nurse will visit each patient participant where they receive their treatment at Week 0, Week 1, Week 4, and Week 8. All participants will have demographic data obtained and the following outcome measures (Table 1):

Weeks	0	1	4	8
Baseline measures (demographics, medical history, vascular history; nursing teams and setting)	~			
Visual analogue pain score (pre, during and after dressing change)	~	~	~	~
Visual analogue pruritus score	~	~	~	~
EQ-5D-5L	~			~
VEINES-QoL	~			~
Patient and Nurses Experience		
 
✓
 
	~	~
questionnaire				
Nurses technical questionnaire		✓	~	~
Photo(s) of both legs	~	✓	✓	✓

Table 1. Outcome measures

- a) Baseline measures (see Appendix 1)
- b) Visual analogue pain score (see Appendix 2)
- c) Visual analogue pruritus score (see Appendix 2)

- d) VEINES-QoL is a patient reported outcome measure score that focuses on lower limb health (see Appendix 2)
- e) EQ-5D-5L is a general quality of life measurement tool (see Appendix 2)
- f) Patient questionnaire for comfort at application, during wear and on removal, fluid handling (see Appendix 3).

During the recruitment process the research team will acts as a contact point and coordinator for patients requiring information and support. If concerns are raised on participants (mental) wellbeing based on the home visits or outcome of the assessments, referral of patients/families on to other professional agencies will be done as appropriate and according to the Trust guideline.

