# Data analysis

# **Refining Programme Theories**

Excel/word documents will be used to store data. The data collected from the recruited participants will be analysed collectively, using descriptive statistics where appropriate and inductively bringing together the various data sources in emerging themes. This will demonstrate how theories evolve in the course of the study. Engagement, involvement, and collaboration between each member of the research team will take place to refine theories to understand when, for whom and in what circumstances are two different types of compression bandages selected in clinical practice. It is hoped and expected that at the end of the study, new guidance for nursing staff will be developed to guide the selection of compression bandages.

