# Safety

There is no anticipated personal safety risk associated with taking part in this study. Appropriate precautions are in place to ensure medical and personal information is kept safe through adhering to appropriate governance regulations.

Participants will be allocated compression bandages that are used for its intended licensed purpose, are considered standard care in the Trust and that are available via NHS procurement routes.

Apart from being allocated to a different type of compression bandage per leg, all patients will be commenced on a compression therapy; therefore, all patients will receive the indicated clinical care they would receive if they were not in the study; they will be cared for in exactly the same manner as they normally would bar that usually both legs would be compressed using the same product for ease of procurement. However, in standard care, it is not unusual to be prescribed two different brands of compression bandages. Some bandage types may be more comfortable at controlling symptoms such as pruritus.

Participants cannot claim payments, reimbursement of expenses or any other benefits or incentives for taking part in this research.

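### The protocol gives two conflicting leg-allocation rules, and the Timeline rule as written permits patients with no paste-versus-dry pair

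*Protocol*

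**What the plan says.** Three places in the protocol bear on how bandages are assigned to legs.

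- **Compression bandage selection procedure:** "one leg will be bandaged in 'paste' compression and one leg in 'dry' compression, through a process of randomisation, using pre-prepared sealed envelopes". The patient is the unit, the pair is fixed, and chance decides only which leg gets which type. Compression level is kept out of the randomisation: "The choice to apply 'full compression' versus 'reduced compression' will be dictated by the aetiology of the ulcer" and by other clinical assessment.
- **Timeline:** "Each leg will be randomised to either" S1F/S1R, S2F/S2R or S3F/S3R. Here the leg is the unit and there are three options. The pairing condition is not repeated.
- **Safety:** "Apart from being allocated to a different type of compression bandage per leg", care is described as otherwise the same as usual. This agrees with the selection procedure.

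The product lists settle which code is which type. The paste list contains one system, S3 ("AndoFlex TLC Calamine (Milliken, USA) - a two-layer compression bandage", with a reduced-compression version). The dry list contains two: S1 ("full compression: UrgoK2 (URGO, France) - a two-layer compression bandage") and S2 ("full compression: Coban2 (3M, USA) - a two-layer compression bandage"), each with a reduced-compression version.

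The protocol gives no allocation ratio, does not say whether the two legs are drawn independently, and does not clearly say how the dry leg comes to receive S1 rather than S2.

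**The concern.** The selection procedure and the Timeline cannot both be followed as written. The first excludes a patient with two dry legs or two paste legs; the second allows both. Whoever prepares the envelopes must make a decision that the protocol does not contain.

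The study contrasts two bandage types, and each patient serves as their own control only if the legs differ in type. A patient with two legs of one type still supplies experience data on that type, but no within-patient contrast.

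Giving precedence to the selection procedure restores the pair but leaves a second gap, because that section randomises type and not brand. The Project summary says that choice of system in usual practice often follows nurse preference. If the dry brand is left open, the same preference could choose the comparator. The Appendix 3 forms would not flag a wrong pair, since any of the three systems can be circled for either leg. The funder also makes the only paste system, which is a further reason for an unambiguous allocation rule.

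**Working it through.** The protocol states no share of patients with a paste-dry pair, so there is no figure to reproduce. The check lists the possible pairs under each reading.

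**Inputs**
- Patients: 40, so 80 legs (Sample and recruitment).
- Systems: S3 is paste; S1 and S2 are dry (the paste and dry bandage lists).
- Compression level (F or R) is set clinically and does not enter the count.
- Assumed, because not stated: equal probability for the three systems, and either independent legs or two different systems per patient.

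**Reading 1: legs drawn independently, 1:1:1.** There are 3 x 3 = 9 equally likely right-left pairs.
- One paste, one dry: 2 x (1/3) x (2/3) = 4/9; 40 x 4/9 = 17.8 patients.
- Both dry: (2/3) x (2/3) = 4/9; 17.8 patients.
- Both paste: (1/3) x (1/3) = 1/9; 4.4 patients.
- No paste-dry pair: 4/9 + 1/9 = 5/9 = 55.6%; 40 x 5/9 = 22.2 patients.
- Binomial chance that more than 20 of 40 patients have no pair: 0.71.

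**Reading 2: the two legs must get different systems.** There are 3 x 2 = 6 equally likely ordered pairs, and 4 of them contain S3.
- One paste, one dry: 4/6 = 2/3; 26.7 patients.
- No pair (S1 with S2): 2/6 = 1/3; 13.3 patients.

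**Reading 3: the Timeline only lists the systems available under the pairing rule.**
- One paste, one dry: 40 of 40. No pair: 0.
- There are 40 paste legs and 40 dry legs, but the split of dry legs between S1 and S2 is not determined.

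**Sensitivity to the ratio.** With independent legs and paste probability p, the share without a pair is 1 - 2p(1 - p). This is 62.5% at p = 0.25, 55.6% at p = 1/3 and 50% at p = 0.5, which is its minimum. Whether the legs are drawn independently therefore matters more than the exact ratio.

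**Number of paste legs.** Under readings 1 and 2 each leg has probability 1/3 of S3, so about 80 x 1/3 = 26.7 paste legs are expected, against 40 under reading 3. The choice of reading thus also changes simple per-leg summaries.

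**The case against.** The best defence is that the Timeline sentence is an outlier and should be read subject to the rest. The section devoted to bandage selection states the pairing rule explicitly, Safety supports it, the research question concerns two types, and envelopes are mentioned only beside the pairing rule. On that view the Timeline merely names the codes a leg may receive, and no patient lacks a pair. This is a fair reading, and it is why no single share can be attributed to the protocol. It does not remove the conflict, because the Timeline uses the language of randomisation for each leg and carries no pairing condition. One can combine the sections into a scheme in which the dry brand is also randomised, but no sentence says so.

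A second defence is that the analysis is not a formal paired comparison: "The data collected from the recruited participants will be analysed collectively, using descriptive statistics where appropriate", together with inductive themes. That stands against any precision argument. A reader might infer that unpaired patients add nothing, or that the standard error of the paired difference rises by 1/sqrt(4/9) = 1.5. Both statements apply only to a within-patient contrast, which the protocol does not formally plan. Appendix 3 collects ratings for each leg, and these are usable from every patient.

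A reader might also infer, from the F and R suffixes, that compression level can be chosen once the allocation is known. The documents do not support that. They do not state the order of the two steps, and the paired codes fit equally well with randomising the system while the level is set clinically.

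**Conclusion.** The inconsistency is real. The Timeline rule, taken as written, permits patients whom the selection procedure and Safety exclude. The share without a paste-dry pair is 5/9 (about 22 of 40) with independent 1:1:1 draws, 1/3 (about 13 of 40) if the two systems must differ, and 0 if the Timeline is only a list within the pairing rule. The protocol does not say which of these applies.

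It is tempting to conclude that more than half of the patients will lack the comparison. That requires independent draws at 1:1:1 or a similarly unequal paste-dry split, and the protocol states neither independence nor a ratio. What holds on every reading is narrower: the envelopes cannot be prepared from the protocol without an added decision, about pairing on the first two readings and about the choice of S1 or S2 on the third.

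**What to change.** Reconcile the Timeline sentence with the selection procedure and Safety by stating one patient-level allocation, held in the sealed envelopes:

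1. Randomise which leg, right or left, receives the paste system (S3).
2. Randomise S1 or S2 for the other leg.

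State the ratio for each step. Full or reduced compression continues to be set clinically, as the selection procedure says.

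The cost is one protocol paragraph and an envelope list prepared to it, with no extra patients or visits. With 1:1 allocation at step 2, each dry brand is used in about 40/2 = 20 patients, so the data on either brand alone will be limited.

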# Criteria for Withdrawal/Discontinuation/exit

- The duration of patient participation in the study is 8 weeks.
- Patient participation in the study will be terminated immediately in case of discomfort or intolerance to zinc or calamine or any allergen present in the dry bandages as per standard procedure.
- Each participant has the right to withdraw from the study at any time without prejudice.
   In addition, the investigator may advise that a participant be discontinued from the study at any time if the investigator considers it necessary for any reason; however withdrawal decisions remain with the participant at all times.
- The investigator may withdraw a subject at any time, for any reason.
- The reasons for withdrawal and discontinuation for any subject shall be recorded.
- Any data and information collected for the subject up until the time of withdrawal or discontinuation, may still be included in the study registry, unless the participant has asked that their data are not to be used. The site shall document all requests by participants regarding their data use.
- Where participants lose capacity to consent during their time in the study, they will be withdrawn from further follow up; however data collected until this point will be retained for use. No further data would be collected, or any other research procedures conducted in relation to the participant.

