# Visual analogue pain

# Pain visual analogue scale Instructions:

"Please think about any **leg pain** you may have had over the past **2 weeks** and put a cross along the scale that best describes it."

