# Pruritus visual analogue scores Pruritus visual analogue scale Instructions:

"Please think about any **leg itching** you may have had over the past **2 weeks** and put a cross along the scale that best describes it."

Not itchy at all

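### Pain is scheduled before, during and after the dressing change, but the only pain scale is a two-week recall that names no leg

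*Protocol*

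**What the plan says.** Protocol, Timeline: "The Research Nurse will visit each patient participant where they receive their treatment at Week 0, Week 1, Week 4, and Week 8". Table 1 ticks the "Visual analogue pain score (pre, during and after dressing change") at all four visits. The list under the table names the tool: "Visual analogue pain score (see Appendix 2").

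Protocol, Appendix 2, holds one visual analogue pain scale with one instruction. The patient is to think of leg pain "you may have had over the past 2 weeks and put a cross along the scale that best describes it". The itch scale beside it is worded the same way: "Please think about any leg itching you may have had over the past 2 weeks". Table 1 schedules itch at the same four visits, but not around the dressing change. Neither instruction says which leg is meant.

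Protocol, Compression bandage selection procedure: one leg is bandaged in paste and the other in dry, "through a process of randomisation, using pre-prepared sealed envelopes". The day of randomisation and of first application is not given. Criteria for Withdrawal/Discontinuation/exit adds: "The duration of patient participation in the study is 8 weeks".

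**The concern.** The schedule and the instrument ask for different things. The schedule wants pain at three moments around one bandage change. The instrument wants a single summary of the preceding fortnight. Asked three times at one visit, the fortnight question is the same question each time, so a table of pain during dressing change built from it would carry the wrong label.

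Patients' opinion on comfort is one of the two stated parts of the study, and patients' difficulty in tolerating compression is given as its inspiration. Pain when a bandage goes on or comes off is a natural place for paste and dry to differ. A scale that does not separate the legs cannot show such a difference at any visit, whatever its recall period. Readings not taken at the visit cannot be recovered in the analysis.

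**Working it through.** The documents give no figure to reproduce here. The check is a side-by-side reading with simple arithmetic.

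**1. Readings scheduled against readings defined.**
- Schedule (Table 1): 3 moments × 4 visits = 12 pain readings per patient, before any split by leg.
- Instrument (Appendix 2): one instruction and one cross, so 1 score × 4 visits = 4.
- The drawn scale is not visible in the text at hand. The wording of the instruction is intact, and it refers to a single scale.

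**2. Can a mark be tied to the change at the visit?**
- Change frequency (Recruiting and Screening): 2 to 3 per week.
- Recall window: 2 weeks.
- Changes per window: 2 × 2 = 4 to 2 × 3 = 6.
- One mark therefore summarises about 4 to 6 changes and all the wear time between them. It cannot be assigned to the period before, during or after one of them.

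**3. Can the mark be tied to a bandage?** Each patient wears two bandage types at once, and the instruction asks about leg pain in general. The result is one score per patient, not one per leg.

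**4. Does another item supply the readings?**
- VEINES-QoL item 7: leg pain over 4 weeks, no leg named.
- EQ-5D-5L: pain or discomfort today, whole person.
- Appendix 3, patient part: for each leg, a yes/no/not-applicable answer on whether the bandage helped with pain and improved comfort, plus free comment. The Timeline describes a patient questionnaire covering comfort at application and removal, but the patient items printed contain no question on either.
- Appendix 3, nurse application form: ease of application and removal as the nurse sees it, not the patient's pain.

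No structured item records the patient's pain around a bandage change.

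**5. Recall window at each visit (secondary point).** Assume the allocated bandages start s days after the Week 0 visit. The share of the 14-day window that precedes them is max(0, 14 − (visit day − s)) / 14.
- s = 0, Week 1 (day 7): (14 − 7)/14 = 7/14 = 50%.
- s = 1 to 3, Week 1: 8/14 to 10/14 = 57% to 71%.
- Week 4 (day 28) and Week 8 (day 56): 0% for every s from 0 to 3.
- Week 0 lies wholly before the allocated bandages, as a baseline should.

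The shares are the same for itch, which has the same recall period.

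**The case against.** The strongest case on the other side has four parts.

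**The study is descriptive.** It is a realist evaluation with no stated primary endpoint or hypothesis test, and pain is one source among several that are brought together into themes. This stands, and it limits the weight of the point. It does not remove the mismatch, because a descriptive summary also needs to measure what its label says.

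**Leg-specific pain is collected elsewhere.** Appendix 3 asks for each leg at Weeks 1, 4 and 8 whether the bandage helped with pain. This also stands, but those items do not isolate application or removal and are not scored on a scale.

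**The scale might be used differently in practice.** Patients could be asked for three marks for their usual pain before, during and after changes over the fortnight. The protocol does not describe how the scale is administered, so this cannot be excluded. The instruction's single cross on a single scale weighs against it, and nothing tells staff to do so.

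**The Week 1 overlap is conditional and confined.** This stands. It depends on a start at Week 0, which the visit schedule and the 8-week participation imply but do not state, and it touches one of the three post-baseline visits. A leg allocated the product it already wore would recall the same bandage throughout.

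A reader might go further and infer that Week 1 reports only half of any true difference between paste and dry. The documents do not support this. The scale as worded yields no between-leg score that could be halved. Even with a per-leg scale, the inference would need equal weighting of all 14 days and no earlier difference between the legs. A reader might also extend the schedule mismatch to itch, but itch is not scheduled around the dressing change and shares only the Week 1 overlap and the missing leg.

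**Conclusion.** The point holds as an internal inconsistency that should be fixed. Table 1 promises pain readings at three moments of the bandage change. Appendix 2 supplies one fortnightly recall covering about 4 to 6 changes, with no leg named. As written, the scale gives neither the scheduled readings nor a comparison of paste with dry. This rests on the protocol's own wording and on its stated 2 to 3 changes per week.

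The Week 1 overlap is a secondary note: 7 of 14 days if the allocated bandages start at Week 0, more if they start later, and none at Weeks 4 and 8. It applies to both pain and itch.

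The documents do not support calling this a critical defect, because the analysis is descriptive and no primary endpoint depends on the scale.

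**What to change.** Reconcile Table 1 with Appendix 2:

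1. Add a short instruction to Appendix 2, asked for each leg: 'pain in this leg right now', marked before, during and after the bandage change at each visit. Point the Table 1 pain row to it.
2. Keep recall scales for pain and itch, but ask each one separately for the right and the left leg. Show recall pain as its own row in Table 1.
3. For the Week 1 overlap, choose one of two courses. Either use a 7-day recall at all visits, so that with a Week 0 start the Week 1 window holds only the allocated bandage, or keep two weeks and state that the Week 1 recall score is not experience of the allocated bandage alone.
4. State the day on which the allocated bandages are first applied.

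The cost is a reworded appendix, an amended table row and a few more marks per visit for the patient. A 7-day recall would also depart from the two-week wording now in Appendix 2, a scale the protocol attributes to a published source. Keeping two weeks with the caveat avoids that.

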# b) Nurse recruitment

The nurses who are applying the compression bandages to the recruited patients will be asked questions about the ease of application. It is not possible to estimate how many nurses will be recruited, as a number of nurses will be looking after the above 40 patients, as per standard care.

- Nursing questionnaire for comfort at application, during wear and on removal, fluid handling (see Appendix 3)
- Nursing questionnaire asking ease of use/application (see Appendix 3).

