# **APPENDIX 3. PATIENT AND NURSE'S EXPERIENCE** PATIENT AND NURSE QUESTIONNAIRE – CLINICAL EXPERIENCE

Bandage used: Right Leg S1F/S1R, S2F/S2R or S3F/ S3R (circle what applies)	S1F = UrgoK2 S1R = UrgoK2 Lite S2F = Coban2 S2R = Coban2 Lite S3F = AndoFlex TLC Calamine S3R = AndoFlex TLC Lite Zinc
FOR THE PATIENT TO COMPLETE	
Please rate the following as your overall experience of circle):	of wearing this bandage (please
Has this bandage helped with your pain?	Yes No N/a
Has this bandage improved your comfort?	Yes No N/a
Has this bandage improved your ability to wear normal footwear and clothes?	Yes No N/a
Has this bandage stayed in place?	Yes No N/a
Has this bandage improved your skin condition?	Yes No N/a
Has this bandage improved your skin irritation?	Yes No N/a
Please add any further comment of your personal experience	
FOR THE NURSE TO COMPLETE	
Prior to last bandage application, was the leg washed with Hydromol mixed in warm water?	Yes No N/a
Prior to last bandage application, was the leg debrided using a debridement cloth or tenatome?	Yes No N/a
Looking at the leg, has this bandage helped improve the leg's skin condition?	Yes No N/a
Looking at the leg, has this bandage reduced the leg's skin irritation?	Yes No N/a
Looking at the leg, has this bandage helped with wound healing?	Yes No N/a

Looking at the leg, has this bandage helped with wound

malodour?

Yes

No N/a

	S1F = UrgoK2
	S1R = UrgoK2 Lite
Bandage used: Left Leg	
	S2F = Coban2
S1F/S1R, S2F/S2R or S3F/ S3R (circle what applies)	S2R = Coban2 Lite
	S3F = AndoFlex TLC Calamine
	S3R = AndoFlex TLC Lite Zinc

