#### FOR THE PATIENT TO COMPLETE

Please rate the following as your overall experience of wearing this bandage (please circle):

Has this bandage helped with your pain?	Yes	No	N/a	
Has this bandage improved your comfort?	Yes	No	N/a	
Has this bandage improved your ability to wear normal footwear and clothes?	Yes	No	N/a	
Has this bandage stayed in place?	Yes	No	N/a	
Has this bandage improved your skin condition?	Yes	No	N/a	
Has this bandage improved your skin irritation?	Yes	No	N/a	
Please add any further comment of your personal experience				
FOR THE NURSE TO COMPLETE				
Prior to last bandage application, was the leg washed with Hydromol?	Yes	No	N/a	
Prior to last bandage application, was the leg washed with Hydromol? Prior to last bandage application, was the leg debrided using a debridement cloth or tenatome?	Yes Yes	No No	N/a N/a	
Prior to last bandage application, was the leg washed with Hydromol? Prior to last bandage application, was the leg debrided using a debridement cloth or tenatome? Looking at the leg, has this bandage helped improve the leg's skin condition?	Yes Yes Yes	No No No	N/a N/a N/a	
Prior to last bandage application, was the leg washed with Hydromol? Prior to last bandage application, was the leg debrided using a debridement cloth or tenatome? Looking at the leg, has this bandage helped improve the leg's skin condition? Looking at the leg, has this bandage reduced the leg's skin irritation?	Yes Yes Yes Yes	No No No	N/a N/a N/a N/a	
Prior to last bandage application, was the leg washed with Hydromol?Prior to last bandage application, was the leg debrided using a debridement cloth or tenatome?Looking at the leg, has this bandage helped improve the leg's skin condition?Looking at the leg, has this bandage reduced the leg's skin irritation?Looking at the leg, has this bandage helped with wound healing?	Yes Yes Yes Yes	No No No No	N/a N/a N/a N/a	

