# NURSE QUESTIONNAIRE – PROFESSIONAL OPINIONS ON APPLICATION

	S1F = UrgoK2		
	S1R = UrgoK2 Lite		
Bandage used: Right Leg			
	S2F = Coban2		
S1F/S1R, S2F/S2R or S3F/ S3R (circle what applies)	S2R = Coban2 Lite		
	S3F = AndoFlex TLC Calamine		
	S3R = AndoFlex TLC Lite Zinc		
On a scale of 1-6 (1 = worst, 6 = best) please rate the following as your overall			

On a scale of 1-6 (1 = worst, 6 = best) please rate the following as your overall clinical experience of using this compression system compared to previously used compression system (please circle):

How easy is it to apply? (i.e. speed, technique required such as simple spirals and visual indicators for correct tension, cutting, tapes)	1	2	3	4	5	6	
How easy is it to remove? (i.e. Wear time – appearance of the bandage post wear – slippage, unwind, worn out areas)	1	2	3	4	5	6	
How 'neat' does it look once it has been applied?	1	2	3	4	5	6	
Is it easy to learn how to apply it?	1	2	3	4	5	6	
Is it easy to teach others to apply?	1	2	3	4	5	6	
Do you like using this bandage			Yes	No N/a	a		

	S1F = UrgoK2
	S1R = UrgoK2 Lite
Bandage used: Left Leg	
	S2F = Coban2
S1F/S1R, S2F/S2R or S3F/ S3R (circle what applies)	S2R = Coban2 Lite
	S3F = AndoFlex TLC Calamine
	S3R = AndoFlex TLC Lite Zinc

On a scale of 1-6 (1 = worst, 6 = best) please rate the following as your overall clinical experience of using this compression system compared to previously used compression system (please circle):

compression system (preuse en cie).							
How easy is it to apply? (i.e. speed, technique required such as simple spirals and visual indicators for correct tension, cutting, tapes)	1	2	3	4	5	6	
How easy is it to remove? (i.e. Wear time – appearance of the bandage post wear – slippage, unwind, worn out areas)	1	2	3	4	5	6	
How 'neat' does it look once it has been applied?	1	2	3	4	5	6	
Is it easy to learn how to apply it?	1	2	3	4	5	6	
Is it easy to teach others to apply?	1	2	3	4	5	6	
Do you like using this bandage			Yes	No N/a	a		

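### The Appendix 3 experience questionnaire has no dedicated item for three of the four things the protocol says it measures, and nine of its 12 closed items per leg cannot separate unchanged from worse

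*Protocol*

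**What the plan says.** Two places in the protocol state what the experience questionnaire covers. Item f of the Timeline section describes a "Patient questionnaire for comfort at application, during wear and on removal, fluid handling (see Appendix 3"). The section on nurse recruitment describes a "Nursing questionnaire for comfort at application, during wear and on removal, fluid handling (see Appendix 3"), and lists a separate questionnaire on ease of use. Table 1 schedules the patient and nurse experience questionnaire at Weeks 1, 4 and 8.

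Appendix 3 prints the form, once for each leg. The patient part opens with "Please rate the following as your overall experience of wearing this bandage (please circle") and its only comfort item is "Has this bandage improved your comfort"? Other items follow the same pattern, for example "Has this bandage improved your skin irritation"? for the patient and "Looking at the leg, has this bandage helped with wound healing"? for the nurse. All closed items are answered Yes, No or N/a. The patient part of each leg's form ends with an open invitation: "Please add any further comment of your personal experience".

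**The concern.** The instrument and its description are both in the protocol and they disagree, so this is not a detail left to a later analysis plan. A team that follows the protocol as printed will reach the end of the study without structured answers on constructs that it has announced as outcomes.

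The answer format adds a second loss. The Project summary gives patients' inability to tolerate compression bandages as the motive for the study, and makes patients' opinions on comfort one of its two parts. The Data analysis section expects new guidance on bandage selection. If an item asks only whether something got better, a bandage that makes a leg mildly worse gives the same closed answer as one that makes no difference.

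The comparison is leg against leg within a patient, so a substitute measure must also say which leg it refers to.

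**Working it through.** No sample size, power or test is involved. The check sets the stated content beside the printed items and then counts response options. The counts use the right-leg form, which is fully legible. The left-leg patient items match it, and the left-leg nurse block is partly broken in the text as read.

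**Step 1: closed items per leg on the clinical experience form.**
- Patient, 6: pain, comfort, footwear and clothes, staying in place, skin condition, skin irritation.
- Nurse, 6: leg washed, leg debrided, skin condition, skin irritation, wound healing, malodour.
- Total: 6 + 6 = 12.

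**Step 2: stated constructs against items.**

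| Construct named in the protocol | Dedicated closed items (of 12) |
|---|---|
| Comfort while applying | 0 |
| Comfort while wearing | 1 (the general comfort item, framed as wearing) |
| Comfort while removing | 0 |
| Fluid handling | 0 |

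Unmatched constructs: 4 − 1 = 3.

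**Step 3: does another instrument fill the gap?**
- The nurse technical form rates ease of application and asks "How easy is it to remove"?, each on a 1–6 scale. These items record how the bandage handles for the nurse, not how it feels to the patient. The nurse recruitment section itself lists comfort and ease of use as two different questionnaires.
- Table 1 lists a pain score before, during and after a dressing change, which would come close to comfort on removal and application. The pain scale printed in Appendix 2, however, asks for recall of leg pain over two weeks. It mentions no dressing change and names no leg.
- Malodour is the item nearest to fluid handling, but it does not ask about exudate or leakage.

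**Step 4: direction of the answers.**
- Patient items asking only about benefit: pain, comfort, footwear and clothes, skin condition, skin irritation = 5.
- Nurse items asking only about benefit: skin condition, skin irritation, healing, malodour = 4.
- Total: 5 + 4 = 9 of 12.

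For such an item, let N legs have a Yes or No answer and let Y of them be Yes. The number of worsened legs can then be anything from 0 to N − Y, and the closed answers cannot narrow it. The selection procedure puts one leg of each of 40 patients in each bandage type, so take N = 40 with no N/a or missing answers. Y is not given in the protocol, so these values are assumptions:

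| Assumed Y | Possible number worse |
|---|---|
| 8 | 0 to 32 |
| 16 | 0 to 24 |
| 32 | 0 to 8 |

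This range shows what the form leaves open. It does not predict how many legs will worsen.

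**The case against.** A reader might infer that the study will hold no information at all on the three constructs, or that the questionnaire cannot record worsening. The documents support neither reading.

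- Each leg's form has a free-text comment. In a realist evaluation that combines descriptive statistics with emerging themes, and plans to publish direct quotations, free text is a planned data source.
- The withdrawal section ends participation for discomfort or intolerance and requires reasons for withdrawal to be recorded, so severe worsening has a route into the data.
- Pain around dressing changes is at least listed in Table 1, and nurses rate application and removal.
- The absence of a Week 0 experience form carries little weight. The items ask about change directly, and at Week 0 the allocated bandage has not yet been worn.
- No hypothesis test depends on these items, so the choice of scale is partly a preference about instruments.

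Much of this stands, and it limits the point to dedicated, structured, leg-specific data. It does not remove the point. Free text does not prompt for the missing constructs. Withdrawal reasons capture only the extreme, and the protocol does not say that the leg concerned is recorded. As printed, the pain and itch scales name no leg, and the two quality-of-life instruments are answered once per patient. The mismatch between description and form is unaffected.

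**Conclusion.** The point holds in this form: three of the four named constructs have no dedicated closed item in the questionnaire said to measure them, and nine of the 12 closed items per leg merge unchanged with worse. Fluid handling is the construct with no evident substitute anywhere in the protocol. For comfort at application and removal the nearest measures exist, but as printed they measure something else or cannot be assigned to a leg. Structured information on milder worsening of one leg is lost and cannot be recovered afterwards.

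This should be corrected, but it does not invalidate the study, because the planned analysis is descriptive and thematic. The conclusion rests on the forms as printed in protocol version 2.3. It does not depend on the assumed counts in the illustration.

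**What to change.** In Appendix 3, for each leg, add patient items on comfort during application, during wear and during removal, and an item on fluid handling (for example leakage). Give the nine directional items a worse/same/better answer and keep N/a. Bring the descriptions in Timeline item f and in the nurse recruitment section into line with the revised form, stating which items the patient answers and which the nurse answers.

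A lighter alternative is to delete the unmeasured constructs from those two descriptions. That removes the contradiction, but it gives up the outcomes and leaves the answer format as it is.

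The cost is about four more items per leg at each of Weeks 1, 4 and 8, and ordinal instead of yes/no summaries, which a descriptive analysis can accommodate. Version 2.3 is dated 18 December 2024 and first recruitment was planned for 1 December 2024, so it cannot be assumed that the form is unused. If recruitment has begun, the change still serves the remaining visits, but answers from the two form versions must be reported separately.
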